Best remission is defined to be the best measured remission status by disease assessment (Molecular CR > Cytogenetic CR > Morphologic CR > CRi > PR > PRi > PD > No Response > Missing). Other categories are defined for CRc (CR + CRi) and disease control (CR + CRi + PR + PRi). The number and percentage for best response will be presented and the number, percentage, and Wilson Score 95% CI will also be presented for the categories of CR, CRc, and disease control. A shift table will be presented between baseline response and best response on-treatment. The order of the best response on-treatment will be Molecular CR > Cytogenetic CR > Morphologic CR > CRi > PR > PRi > PD > No Response > Missing. And the response of baseline will be classified as Molecular CR, Cytogenetic CR, Morphologic CR, CRi, Stable disease (SD). Patients who are not classified in any of Molecular CR, Cytogenetic CR, Morphologic CR or CRi will be classified as stable disease (SD). If a patient could be classified in multiple categories at baseline, the response will be chosen in the following order: Molecular CR > Cytogenetic CR > Morphologic CR > CRi > SD. All summaries will be presented overall and by dose cohort.

A by-patient listing of IWG assessment will be provided.

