## 8.6.4. Additional Exploratory Endpoints

For solid tumor patients the following endpoints will be calculated as follows:

• Progression-free survival (PFS) is defined as the time in weeks from first dose date to the date of progression or the date of death due to any cause. Patients who are alive and have not progressed by the date of analysis data cut-off will be censored at the last free evaluable tumor assessment date based on investigator

assessment. Patients with missing protocol scheduled tumor assessment(s) prior to radiologic disease progression will be considered as having disease progression on the date of the actual assessment of disease progression.

- Time to progression (TTP) is defined as the time in weeks from first dose date to the date of observed disease progression. Patients who do not have disease progression by the date of analysis data cutoff will be censored at the date of last evaluable tumor assessment based on investigator assessment.
- Duration of response (DOR) is defined as the time in weeks from the first date of response to date of first progression of disease or death in the subset of patients with an objective response of irCR or irPR. Patients who respond and have not progressed (as evaluated by investigator assessment) while on study or die will be censored at the date of their last evaluable tumor assessment. Duration of response is calculated only for patients with an objective response.

For AML patients, the following endpoints will be calculated as follows:

- Relapse is defined as
  - an investigator assessment following CRc becoming PR, PRi, PD, or No Response. The date of the worsening disease assessment will be the relapse date; or
  - an investigator assessment following PR or PRi becoming PD or No Response. The date of the worsening disease assessment will be the relapse date
- Duration of CRc: Time, in weeks, from first CRc until documented relapse and is only defined for patients who achieve CRc. Patients who die without report of relapse are considered non-events and censored at their last relapse-free disease assessment date. Patients who come off study for an allogeneic HSCT will be considered non-events and censored at the time of treatment discontinuation. Other patients who do not relapse on study are considered non-events and censored at the last relapse-free assessment date.

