- Duration of disease control: Time, in weeks, from first of either PR, PRi or CRc until documented relapse of any type and is only defined for patients who achieve CRc, PR or PRi. Patients who die without report of relapse are considered non-events and censored at their last relapse-free disease assessment date. Patients who come off study for an allogeneic HSCT will be considered non-events and censored at the time of treatment discontinuation. Other patients who do not

relapse on study are considered non-events and censored at the last relapse-free assessment date.

 Time to progression for AML (TTPAML) is defined as the time in weeks from first dose date to the date of observed disease progression (see Section 8.6.2.2).
 Patients who do not have disease progression by the date of analysis data cutoff will be censored at the date of last evaluable disease assessment based on investigator assessment.

For all patients, and by disease group, the following endpoints will be calculated as follows:

- Date of last contact will be defined as the latest of the treatment discontinuation date, last dosing administration date, last disease assessment date, end of study or the death date.
- Overall survival (OS): Time, in months, from first dose date until the date of death. Patients who do not die are censored at their date of last contact. Survival status is captured after the end of the treatment period and is also considered in determining overall survival.
- The specified time-to-event endpoints will be summarized graphically with Kaplan-Meier (KM) estimates of the survivor function and the number of patients at risk for selected timepoints. Additionally, the figures will include the median of the survival distribution and the 95% CI generated using the method of Brookmeyer and Crowley (Brookmeyer-1982). Time-to-event endpoint data will be listed grouped by tumor group. Each of the KM figures will be repeated for the Safety population as additional exploratory analyses.

For all the KM plots, the SAS output will be saved in Statistics Appendix in TFL.

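### In AML, a step down from CRc to PR or PRi ends the duration of disease control, although PR and PRi are themselves disease control

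*SAP*

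**What the plan says.** Three parts of the SAP bear on this.

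- **The category.** Section 8.6.2.2 sets out the AML groupings: "Other categories are defined for CRc (CR + CRi) and disease control (CR + CRi + PR + PRi". A patient in PR or PRi is therefore in disease control.
- **The relapse rule.** Section 8.6.4 gives two kinds of relapse. The first is "an investigator assessment following CRc becoming PR, PRi, PD, or No Response". The second is "an investigator assessment following PR or PRi becoming PD or No Response".
- **The duration.** In Section 8.6.4 the duration of disease control is counted "from first of either PR, PRi or CRc" and runs "until documented relapse of any type and is only defined for patients who achieve CRc, PR or PRi". The words on type bring in both kinds of relapse.

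Section 8.6.4 also has a separate duration of CRc, which starts at the first CRc and ends at documented relapse. Section 6.5, which lists the endpoints, does not mention a duration of disease control. It lists a duration of response made up of CRc plus partial remission, without PRi.

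**The concern.** The event that ends the duration does not match the state whose duration is being measured. A patient in CRc whose next assessment is PR or PRi has relapsed under Section 8.6.4, so the clock stops, yet the same assessment counts as disease control under Section 8.6.2.2. Such a patient can score a shorter duration than one who never got beyond PR, although both left disease control at the same visit.

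There is also a redundancy. If a patient's first response is CRc, the duration of CRc and the duration of disease control have the same start, the same event and the same censoring rules. For that patient the second endpoint repeats the first.

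At stake are the Kaplan-Meier curve and the median with its 95% CI for this endpoint. Only AML patients with a response enter it, and planned AML numbers are small: Section 4.1 asks for at least 6 evaluable patients of each tumor type in Part 1 and at least 4 AML patients at each Part 2 dose level. One or two affected patients could move the median.

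**Working it through.** The plan gives no figure for this endpoint, so there is none to reproduce. The check applies the SAP's definitions to every possible category change and then to example paths.

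**1. Category changes that count as relapse (Section 8.6.4)**

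- From CR or CRi to PR, PRi, PD or No Response: 2 × 4 = 8.
- From PR or PRi to PD or No Response: 2 × 2 = 4.
- Total: 8 + 4 = 12.

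The patient is still in a disease-control category after 4 of the 12: CR to PR, CR to PRi, CRi to PR and CRi to PRi (2 × 2 = 4). In the other 8 the new category is PD or No Response, and the end of disease control is scored correctly.

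**2. Example paths**

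The paths are assumed, with marrow results every 8 weeks.

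- Duration as written = week of first relapse of either kind − week of first CRc, PR or PRi.
- Time in the category = week of first PD or No Response − week of first CRc, PR or PRi.

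| Path | As written | Time in the category |
|---|---|---|
| A: PR from week 8, PD week 32 | 32 − 8 = 24 weeks | 32 − 8 = 24 weeks |
| B: PR week 8, CR week 16, PR week 24, PD week 32 | 24 − 8 = 16 weeks | 32 − 8 = 24 weeks |
| C: CR week 8, PR weeks 16 to 32, PD week 40 | 16 − 8 = 8 weeks | 40 − 8 = 32 weeks |
| D: PR weeks 8 to 32, PD week 40 | 40 − 8 = 32 weeks | 40 − 8 = 32 weeks |

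A and B spend the same 24 weeks in disease control, but B scores (24 − 16)/24 = 33% less. C and D spend the same 32 weeks, but C scores 8.

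**3. Can a step down to PR or PRi occur without being PD?**

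Section 8.6.2.2 defines PD by a blast increase of at least 50% together with an increase of at least 10%. It does not say whether the reference is baseline or nadir. I read the 10% as percentage points, since a relative 10% would add nothing to the 50% rule.

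Take baseline 40% blasts, CR at 2%, then 8%. Against baseline this is a fall of (40 − 8)/40 = 80% into the 5% to 25% range, so the blast criterion for PR or PRi is met. It is not PD against baseline, because blasts have fallen. It is not PD against nadir, because 8 − 2 = 6 points is under 10. The step down is therefore possible under either reference.

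The reference does limit how often it can occur. With baseline 60% and CR at 4%, a later 14% meets the PR blast threshold, but against nadir it also meets PD (14 − 4 = 10 points, and more than 50% up). If the investigator records PD, the duration ends correctly. The problem is confined to visits recorded as PR or PRi.

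**The case against.** The strongest defense is that the rule is deliberate. The wording takes in both kinds of relapse on purpose, and Section 6.5 calls the endpoint a duration of response. Ending a response duration when complete remission is lost is a defensible convention. That would justify the rule under that name. It does not justify it under the name disease control, which Section 8.6.2.2 defines to include PR and PRi, and loss of CRc already has its own endpoint. For solid tumors, Section 8.6.4 ends duration of response at progression or death, so a step from irCR to irPR is not an event there.

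A second objection is frequency. PR and PRi need a marrow aspirate, and the footnotes to the schedules of assessments leave AML marrow sampling after baseline largely to clinical indication. This stands: the documents give no basis for saying how many patients would follow path B or C.

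A third is that the by-patient listings let a reader reconstruct each path. They do, but the curve and median would still carry the mismatch.

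Two stronger readings are tempting, and the documents do not support them.

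- **That the rule gives the deepest responders the shortest durations.** A patient who stays in CRc, or goes from CRc straight to PD or No Response, is not penalized. Only the step down through an assessed PR or PRi is affected.
- **That AML time to progression is also wrong because it ignores relapse.** In 8 of the 12 relapse changes the new category is not PD, so a visit can be a relapse without being a progression event. But Section 8.6.4 measures this endpoint "to the date of observed disease progression (see Section 8.6.2.2", which points to a defined PD category. It covers all AML patients from first dose, whereas relapse is used for durations among responders. Two endpoints with different events may differ at one visit. Nor is every apparent gap real: with baseline 40%, CR at 2% and then 30%, there is no PD against baseline, but there is against nadir (30 − 2 = 28 points), and the reference is unstated. Making relapse a time-to-progression event would also import the fault: path B would fall from 32 to 24 weeks while path A stayed at 32.

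**Conclusion.** The concern holds for the duration of disease control only. Followed exactly, the SAP scores a patient who steps down from CRc to an assessed PR or PRi as having lost disease control while still in that category. This applies to 4 of the 12 relapse changes. In the examples it costs 8 of 24 weeks (path B) and 24 of 32 weeks (path C).

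The contradiction between Sections 8.6.2.2 and 8.6.4 rests on the text alone. The size rests on assumed paths with 8-weekly marrow results and on the investigator recording PR or PRi at the step down. The number of patients affected cannot be estimated from the documents.

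Severity is low. The endpoint is exploratory and descriptive, with no test or decision rule attached. The DLT and MTD analysis, the sample size and the best-response proportions are unaffected.

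**What to change.** 1. In Section 8.6.4, define the event for duration of disease control as the first assessment of PD or No Response after CRc, PR or PRi, and state that CRc becoming PR or PRi is not an event for this endpoint.
2. Align the censoring sentence: patients without an event are censored at the last assessment before any PD or No Response. If the present reference to relapse were kept, a patient who stepped down to PR and never progressed could be censored at the last CRc visit. The transplant censoring rule need not change.
3. Keep CRc becoming PR, PRi, PD or No Response as the event for duration of CRc only.
4. Use one name and one response set for the endpoint in Sections 6.5 and 8.6.4, and say whether PRi is included.
5. Leave AML time to progression as it is.

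Under this definition paths A and B both score 24 weeks, and paths C and D both score 32. The cost is a few sentences in the SAP and one derived variable. The investigator's AML assessments are already collected and listed, so no new data or visits are needed.

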#### 4. STUDY DESIGN

# 4.1. General Description

This is a Phase 1, open-label, dose-escalation, 2-part study in adult patients with advanced malignancies known to overexpress the WT1 protein. The study will primarily evaluate DLT and define the MTD of WT2725 Dosing Emulsion during the DLT Evaluation Period, which extends from the day of the first dose of study drug to just prior to the fifth dose (Days 1 - 29). In addition, antitumor activity and biomarkers indicative of immune response will be evaluated from the first dose until discontinuation of the patient from the study. An end of study assessment will take place within 28 days after the last dose of study drug and prior to the start of alternate antineoplastic therapy.

The initial patients in each dose escalation cohort will be enrolled at least one week apart to evaluate initial safety from the first 2 patients, then a "rolling-six" design will be employed that allows accrual of 2 to 6 patients concurrently in each dose escalation cohort.

In Part 1 of the study, the 0.3 mg cohort will be conducted first. After safety and tolerability have been established for the first cohort, enrollment of subsequent patients will be conducted sequentially in subsequent cohorts and continue until the MTD or all planned cohorts are attained. Enrollment of each cohort may include patients with any of the eligible tumor types (see below). Enrollment of the highest tolerable dose cohort (MTD or highest planned cohort) will continue until there are at least 6 patients total in the study with each tumor type that are evaluable for DLT, biomarkers, and response. This dose is considered the recommended phase 2 dose (RP2D). Enrollment of up to 3 RP2D cohorts of 10 patients each of a specific tumor type may take place at this dose in order to further characterize the safety and efficacy of WT2725 Dosing Emulsion at this

dose in these subsets of patients. Additional dose escalation cohorts after the initial expansion cohorts may be enrolled if a MTD has not been determined and significant signs of toxicity have not been observed in the expansion cohorts.

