- Tumor assessments will be by irRC for solid tumors, modified IWG for AML, and/or standard tumor markers as appropriate eg, CA-125 for ovarian carcinoma and quantitative RT-PCR for WT1 transcript for AML. Perform every 8 weeks after 1st dose or more frequently as clinically indicated. Tumor markers drawn from peripheral blood samples should be assessed every 4 weeks after the 1st dose. This assessment may be performed ± 7 days of the scheduled assessment but must be completed before the next planned administration of study drug. For patients with AML if no other measurable disease then bone marrow aspirations/biopsies should follow the general post-transplant biopsy schedule or other clinical site guidelines. Progressive disease requires confirmation by a repeat, consecutive assessment at least 4 weeks after the date of first documentation, unless rapid clinical deterioration is seen. For patients with glioblastoma, progressive disease should additionally be confirmed by SPECT, perfusion MRI, MRI spectroscopy or C-14 methionine PET or pathology from available surgical/biopsy specimens to differentiate from pseudoprogression. For patients with ovarian cancer that express CA-125, progressive disease should additionally be confirmed by CA-125 (≥ 2x higher of ULN or on study nadir). For patients with AML, bone marrow aspirations/biopsies are scheduled when clinically indicated, however peripheral blood should be assessed for blasts and WT1 transcript at least at every 4 weeks or more frequently as clinically indicated.
- n Tumor markers drawn from peripheral blood samples should be assessed at least every 4 weeks after the 1st dose but may be performed more frequently (For other tumor assessments, perform every 8 weeks after 1st dose or more frequently as clinically indicated).
- o Following the End of Study visit, patients will be contacted every 3 months to evaluate disease progression, if not already reached, and survival.

Table 3: Schedule of Assessments for Screening and Vaccine Induction Phase – Part 2

	Scree								e Inducti	on Phase a,b,t					
	within 14/21			1 st dose		2 nd dose	3 rd dose	4 th dose		5 th dose		6 th dose	7 th dose	8 th dose	9 th dose

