# 8. STATISTICAL ANALYSIS

In this section and all after, when tables are presented by posttreatment visits, the last visit will be the visit at the end of study. When applicable, visits after the start of the maintenance phase and unscheduled visits will be included in a summary of maximum and minimum values observed for each patient's posttreatment visits, i.e., the minimum and maximum values are based on all the post treatment visits.

In general descriptive statistics for continuous variables will be summarized by the mean, standard deviation, 25th percentile, median (50th percentile), 75th percentile, minimum and maximum values. When continuous variables are displayed for less than 3 patients, only the number of observations will be presented. Categorical variables will be summarized using counts and percentages.

All raw data will be presented to the original number of decimal places. The means and medians will be presented to 1 more decimal place than the raw data. The standard deviations will be presented to 2 more decimal places than the raw data.

Baseline will generally be defined as data obtained as the last non-missing value prior to the first dose of study drug, i.e., including the pre-dose assessment on Day 1, assessments during screening and other assessments prior to the first dose of study drug.

AE tables and laboratory tables will be presented by visits and by tumor group. Tumor groups are defined as groups of overall, solid tumor, and AML patients.

Unless otherwise stated, summaries will be produced by dose cohort, which is defined as the intended and starting dose to which the patient was enrolled.

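### The OS rule counts deaths found in 3-monthly follow-up but censors survivors at a last-contact date that omits those contacts, biasing the exploratory OS curve downward

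*SAP*

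**What the plan says.** SAP 8.6.4 defines OS as "Time, in months, from first dose date until the date of death". The censoring rule is: "Patients who do not die are censored at their date of last contact". The date of last contact is the "latest of the treatment discontinuation date, last dosing administration date, last disease assessment date, end of study or the death date". The OS bullet then adds: "Survival status is captured after the end of the treatment period and is also considered in determining overall survival". It gives no date to go with that status.

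The SAP uses the term End of Study for a visit close to the last dose. Section 4.1 says: "An end of study assessment will take place within 28 days after the last dose of study drug". Section 8 says that in tables by visit "the last visit will be the visit at the end of study". Survival follow-up starts only afterwards. Footnote o to Tables 2 and 4 in Section 6.1 reads: "Following the End of Study visit, patients will be contacted every 3 months to evaluate disease progression, if not already reached, and survival". The Protocol amendment history (Amendment No. 3) says this follow-up was added to assess progression and survival more completely.

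For progression-free survival, Section 8.6.4 names a cut-off: "Patients who are alive and have not progressed by the date of analysis data cut-off will be censored". Both time-to-progression definitions also name one. The OS bullet does not.

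OS is an additional exploratory endpoint (Section 6.5), summarized for all patients and by disease category. The planned outputs are Kaplan-Meier curves with the median and its 95% confidence interval.

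**The concern.** Kaplan-Meier assumes that censoring tells us nothing about later survival. Under this rule it does. Suppose two patients stop treatment in the same month and both are reached by follow-up a year later. If one has died, that patient stays in the risk set until death and counts as an event. If the other is alive, that patient is removed from the risk set back at the End of Study visit. Being censored early therefore depends on being found alive later.

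The patients affected are mainly survivors who had already progressed by the End of Study visit. For patients without progression, a follow-up contact also evaluates progression and may count as a disease assessment, which is on the list. Patients still on treatment are little affected.

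At stake are the reported OS curve, its median and its confidence interval. With no comparator and no test, a reader has only these figures to judge survival by.

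**Working it through.** The plan states no OS figure, so there is none to reproduce. The check has three parts.

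**1. What the rule does to a patient alive at the cut-off, off treatment and already progressed**

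| Date on the last-contact list | Where it falls for this patient |
|---|---|
| Last dose, treatment discontinuation | At or before the End of Study visit |
| End of study | Within 28 days of the last dose |
| Last disease assessment | No later than about the End of Study visit; follow-up looks for progression only if not already reached |
| Death | None |

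The latest of these is about the End of Study visit, however many later contacts confirm the patient alive. If the same patient dies, the OS time runs to the death.

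**2. Hypothetical ten patients**

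Three die at months 6, 8 and 10. Five progressed survivors have End of Study visits at months 3, 3, 4, 4 and 5. Two unprogressed survivors are followed to month 18.

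- As written: the five progressed survivors have left before month 6, so the numbers at risk at the deaths are 5, 4 and 3. 12-month OS = 4/5 × 3/4 × 2/3 = 0.40. The curve first reaches 0.50 or below at month 10, so the median is 10 months.
- All seven survivors censored at an 18-month cut-off: the numbers at risk are 10, 9 and 8. 12-month OS = 9/10 × 8/9 × 7/8 = 0.70. The median is not reached.

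**3. Simulation**

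None of these inputs is in the documents; all are assumptions:

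- exponential OS, median 6, 12 or 18 months;
- exponential time to End of Study, median 3 or 5 months, minimum 1;
- cut-off uniform on 0.5 to 1.5 times a mean of 12 or 24 months;
- correlation 0 or 0.6 between time to End of Study and OS;
- 0% or 30% of patients whose contacts count as disease assessments.

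This gives 3 × 2 × 2 × 2 × 2 = 48 scenarios of 100,000 patients each. Deaths by the cut-off are events. Only the censoring date of survivors changes between columns.

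| Result | As written | Last 3-monthly contact added | Common cut-off |
|---|---|---|---|
| Median, truth 6 months | 5.0–6.0 | – | – |
| Median, truth 12 months | 7.3–11.0 | 11.0–12.0 | 11.9–12.1 |
| 12-month OS, truth 50% | 19–47% | 47–50% | 50% |
| Median, truth 18 months | 8.7–14.7 | 15.1–17.7 | see note |
| 12-month OS, truth 0.5^(12/18) = 63% | 27–58% | 60–63% | 63% |

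Note: with a true median of 18 and 12 months' mean follow-up, the common-cut-off median lies at the edge of follow-up and is sometimes not reached, so 12-month OS is the better comparison there.

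At a true median of 12, between 23% and 46% of all patients are alive at the cut-off with End of Study already past. These are the patients open to early censoring.

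A second simulation used different assumptions: treatment time independent of OS with median 2 or 4 months, accrual over 36 months, and minimum follow-up 0 or 12 months. For a true median of 12 it gave 8.4–10.2 as written and 11.6–12.0 with the contact date added. In small-sample runs (median treatment time 3 months, cut-off 6 to 36 months after first dose), the as-written median was 9.0 at both n = 20 and n = 70, against 11.4 and 11.7 with the contact date. The bias is therefore not a small-sample effect.

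**The case against.** **The survival-status sentence may already repair the rule.** Any death is an event under the definition, so a sentence saying that post-treatment status is considered could be meant to let alive dates update the censoring date. That is a possible intention. But the sentence supplies no date and does not amend an explicit list, and two programmers could code it differently.

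**End of study in the list is not defined there.** It could mean the end of each patient's participation, and the bias would then disappear. This is weak, because Sections 4.1, 6.1 and 8 use the term for the visit before follow-up begins.

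**The cut-off may be a drafting omission.** It is named for three other endpoints and is presumably one analysis-level date. The duration endpoints omit it too. This is fair, but the OS rule should still say so.

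**The largest errors come from short follow-up.** This stands. At a true median of 12, the as-written median is 9.1–11.0 with a 24-month mean follow-up and 10.4–11.6 with 36 months. The amendment history shows the recommended phase 2 dose had been identified by 31 May 2013 and Part 2 was added on 3 December 2014, about 18 months later. Many Part 1 patients may therefore have longer follow-up, although Part 2 patients could have less. The bias shrinks as more patients have died by the cut-off and is nil if all have. The ten-patient example is also built to show the effect clearly.

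**Adding the contact date does most of the work.** With a 24-month mean follow-up and a true median of 12 it gives 11.8–12.1. The common cut-off and status check remove what remains, which matters mainly when follow-up is short.

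**Conclusion.** The concern holds. Read literally, the rule makes censoring depend on outcome, and the resulting error in the OS curve is downward. The direction follows from the rule itself, provided some progressed patients are alive after their End of Study visit and some deaths occur later. The size rests wholly on assumed survival, treatment time and follow-up: small if survival is short or nearly all patients have died, and several months on the median if a sizeable share are long-term survivors. OS is exploratory and carries no test or decision rule, so the DLT and MTD conclusions stand. The change should still be made before the OS analysis, because the rule as written can produce a misleading median and confidence interval.

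**What to change.** In SAP 8.6.4:

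1. Add to the date-of-last-contact list the last survival follow-up contact at which the patient was known to be alive, and state that end of study in that list means the End of Study visit.
2. State one OS data cut-off applied alike to deaths and survivors. Deaths after it are not events, and patients confirmed alive at or after it are censored at it.

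Check the survival status of all patients around the cut-off. Without this, survivors are censored at their last contact while deaths between that contact and the cut-off still count, which leaves a smaller downward bias.

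The cost is two sentences and slight programming. It must be confirmed that the CRF, which is not among the documents, records the date of each alive contact. The status check adds some site work.
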